of interest (ROIs) identified with standard univariate methods (i.e., a GLM) [37]. Notably, head-to-head comparison of BOLD signal intensity levels vs. the information contained in this signal (as inferred from MVPA) indicates that direct interpretation of the former can be misleading: 1) activity levels are not always sensitive to which items are in vs. out of the focus of attention (nor, indeed, to which are in vs. out of a trial's stimulus set); and, 2) activity levels in a “category-specific” ROI can remain elevated above baseline even when the MVPA indicates the absence of information related to this category (Fig. 2). This second finding has been extended to the level of item representation in two other fMRI studies from the PI's group, in which frontal and parietal regions show sustained delay-period activity, but MVPA indicates that this activity does not represent which of 3 or 4 directions of motion is in memory [17, 58]. Reminiscent of previous findings [24, 62], however, trial-specific stimulus information was found to be represented during the delay period in early visual areas whose activity was not above baseline levels [17, 58].

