
Sub-study B: Behavioral task, ECoG recording, and data processing.

Experimental procedure. The study consists of two sessions on different days. The generic task design will be as follows: In the first session, each trial begins with a fixation cross and serial presentation of two sample items, followed by a brief delay (Delay1pre-cue), followed by a cue (Cue1) indicating which item will be tested first, followed by an additional delay (Delay1post-cue), followed by a memory probe

requiring a “same/different” response (Probe1) followed by Delay2pre-cue, Cue2, Delay2post-cue, and Probe2. The timing will be as follows: Fixation (.5 sec); Sample1 (.5 sec); ISI (.1 sec), Sample2 (.5 sec); Delay1pre-cue (.5 sec), Cue1 (.5 sec), Delay1post-cue (2.5 sec), Probe1 (2 sec); Delay2pre-cue (.5 sec); Cue2 (.5 sec); Delay2post-cue (2.5 sec); and Probe2 (2 sec). Thus, total time per trial = 12.6 sec. (Note that the duration of the Delaypost-cue epochs is necessitated by the fact that behavioral [31, 45] and EEG data [31] indicate that it takes between 1-2 sec for an item to transition from AMI to UMI.). This timing will allow for the collection of 96-106 trials within a span of 30 min, a block that can be interrupted and restarted as needed to suit the comfort of the patient. (Previous experience from ECoG studies performed by colleagues of the PI who are based at the University of California indicates that the “20-min mark” is a conservative estimate of the duration of a testing session that a patient can be expected to tolerate; many patients can tolerate either longer sessions, or multiple sessions separated in time.) Critically, the ECoG study that discovered and characterized the phase-encoded selection mechanism that we will investigate in the present study [70] made this discovery in data from four patients, with a design that yielded 40-50 trials/condition/patient; thus our design, intended to collect a minimum of 96 trials, will be adequately powered to detect effects of interest at the single-subject level. (SNR of ECoG signals will be considered further along in this section.)

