For each stimulus domain, each sample stimulus will only appear once in the experiment. The stimuli were determined from previous studies using similar tasks to yield 75-90% correct performance in an independent set of healthy young adults. On each trial, two stimuli from the three categories will be presented, and cuing will be randomly determined, such that on each trial one item serves as the AMI, one as the UML, and one as the “irrelevant” category (i.e., the category that was not presented on that trial).

- Face stimuli will be photographs of highly discriminable faces with different genders and races. The probe stimuli will either be a same face, or a difference face with the same gender and race.

- Scene stimuli will be photographs of highly discriminable natural scenes. The probe stimuli will either be a same scene, or a difference scene from the same scene category.
- Word stimuli will be words that have homonyms. The probe stimuli will either be the homonym of the sample word, or a different word.

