Stage 2. Having identified stimulus-selective electrodes in Stage 1 of our analyses, Stage 2 will effect the test of the phase-encoded selection hypothesis. Specifically, we will test the hypothesis that UMLs and AMIs will each be maintained in an active state, as manifested by above-baseline high-gamma power, but that the amplitude of this high-gamma power will be markedly higher for AMIs. Furthermore, this differential level of high-gamma power will be explained by the fact that the (pattern of) electrodes representing the AMI will exhibit higher interregional PAC than will the UMI. Because Voytek and colleagues [69] have shown that PAC in posterior regions tends to be anchored in the alpha band (as contrasted with a bias toward theta-paced PAC in frontal cortex), we expect that the attention-related changes in interregional PAC in ITS, mid fusiform gyrus, VO1, and/or STS, may also be concentrated in the alpha band. Assuming that we do find evidence for a phase-encoded selection mechanism in our working memory task, an important question will be to determine the source of the low-frequency oscillation clocking the predicted selection-related increase in interregional PAC. Our *a priori* working hypothesis is that this will be the “posterior alpha” that is prominent in EEG electrodes

over parietal cortex, strongly associated with visual attention (e.g., [50, 59, 67]), and widely assumed to be generated by thalamocortical circuits encompassing the caudal intraparietal sulcus.

One important point highlighted in our research plan is the fact that study [70], on which the data analysis plan of the present protocol was based, is “limited” to four patients, and to 20-30 trials/condition/patient, it nonetheless featured sufficient power to support, for example, trial-by-trial prediction of behavioral RT, and msec-level resolution of the onset of event-related phase-encoding (i.e., of phase-encoded selection).

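### Sub-study B, Stage 2: high-gamma power above an undefined baseline does not by itself show that unattended items are actively held, and the not-presented category, the built-in control, is not used

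*Combined protocol and SAP*

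**What the plan says.** Specific Aims/Study Objectives poses a choice: either UMIs have no elevated neuronal activity, or they have it at a scale that noninvasive recording misses. Under Statistical Considerations, Sub-study B, Stage 2 takes this up with the hypothesis that "UMLs and AMIs will each be maintained in an active state, as manifested by above-baseline high-gamma power". Two further predictions follow: that "the amplitude of this high-gamma power will be markedly higher for AMIs", and that the "electrodes representing the AMI will exhibit higher interregional PAC than will the UMI" (PAC is phase-amplitude coupling). No part of the document says which period or condition serves as baseline for this test.

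Background and Significance reports, from the group's own fMRI work, that activity in a category-specific region "can remain elevated above baseline even when the MVPA indicates the absence of information related to this category". It adds that "frontal and parietal regions show sustained delay-period activity, but MVPA indicates that this activity does not represent" the motion direction being remembered. It also reports the reverse case: item information in early visual areas whose activity was not raised.

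In Sub-study B each trial shows items from two of three categories (faces, scenes, words). One becomes the AMI and one the UMI. The third is the irrelevant category, "the category that was not presented on that trial". Stage 2 does not mention it.

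**The concern.** For the UMI, power above baseline is the only stated criterion. If the delay period raises high-gamma power at a category's electrodes whatever their role on that trial (through general engagement, for example), the UMI would pass although nothing about it is represented. The Background describes that pattern in fMRI. Choosing stimulus-selective electrodes in Stage 1 does not remove the problem, because the Background reports it in regions chosen as category-specific.

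The omission also departs from the protocol's own logic. The Background treats attended, ignored and irrelevant locations in Sub-study A as the same distinction, in form, as AMI, UMI and trial-irrelevant items. Statistical Considerations makes ignored against irrelevant the key comparison of Sub-study A. Sub-study B has the matching control and plans no comparison with it.

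At stake is one side of the question in the Specific Aims. A false finding of an active UMI would be read as overturning the group's earlier null results.

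**Working it through.** The plan states no alpha, effect size, SD or numerical power for this test, so there is no figure to reproduce. The check has three steps.

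**1. What each comparison can show.** At a category's selected electrodes, let g be the rise over baseline common to all roles in the delay. Let a and s be the extra activity when the category is the AMI or the UMI.

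| Comparison | Estimates | If the UMI carries nothing (s = 0) |
|---|---|---|
| UMI − baseline (planned) | g + s | g, positive whenever g > 0 |
| AMI − UMI (planned) | a − s | a, so the prediction is still met |
| UMI − not presented (available) | s, if g is equal in both roles | 0 |

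The PAC prediction is also AMI against UMI, so the second row applies to it too.

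**2. Size of the problem (illustration).** The assumptions are mine: independent normal trials, SD 1, two-sided 0.05 with only positive results counted (nominal 2.5%), and balanced roles. Trials per role are 96/3 = 32 or 40/3 ≈ 13. The UMI signal is s = 0. The rates below come from 20,000 simulated data sets per row, using a one-sample t-test for UMI against baseline and a two-sample t-test for UMI against not-presented.

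| Assumed lift g (SD) | UMI > baseline, n = 32 | UMI > baseline, n = 13 | UMI > not presented, either n |
|---|---|---|---|
| 0 | 2.5% | 2.3% | 2.4–2.6% |
| 0.2 | 20% | 9% | 2.4–2.5% |
| 0.3 | 38% | 17% | 2.3–2.5% |
| 0.5 | 78% | 38% | 2.5–2.6% |
| 0.8 | 99% | 76% | 2.4–2.5% |

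Hand check by normal approximation, Φ(g√n − 1.96): for g = 0.3 and n = 32, 0.3 × 5.657 − 1.96 = −0.263, and Φ = 0.396. The simulated t-test gives 38%.

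**3. Precision of the alternative.** For a true UMI-specific shift d (in SD), power ≈ Φ(d√(n/2) − 1.96). For d = 0.7 and n = 32, 0.7 × 4 − 1.96 = 0.84, and Φ = 0.80.

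| d (SD) | n = 32 per role | n = 13 per role | n per role for 80% |
|---|---|---|---|
| 0.5 | 52% | 25% | 63 |
| 0.7 | 80% | 43% | 33 |
| 1.0 | 98% | 72% | 16 |

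**The case against.** **Stage 1 already tests information.** Classifiers trained on the sample period are fed delay data, with cross-validated decoding of the post-cue delays as an alternative. A three-category classifier implicitly includes the absent category. This is a real mitigation. But the plan calls Stage 1 exploratory, uses it to find the code and pick electrodes, and writes no rule for UMI against irrelevant. The Stage 2 criterion does not depend on one.

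**The contrary evidence is fMRI.** This stands as a limit. BOLD findings show that the inference can fail, not that it fails for high-gamma ECoG at selected electrodes. A reader might infer that the planned test is bound to mislead; the documents do not support that.

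**Above-baseline power is only part of a hypothesis.** This is true: the stated aim is phase-segregated representation and phase-encoded selection, and the plan does not call power proof. It is still the only operational criterion given for an active UMI.

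**The replacement is not clean.** This stands. The contrast removes only delay activity common to both trial types. On UMI trials the category has just been shown, so residual sample-evoked response remains. Non-specific activity may also differ by role: the Background treats a parallel question about alpha activity as open. It would therefore be too strong to say that the contrast isolates item-specific activity. It also remains a test of power level and can miss an item represented without raised activity.

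**A contaminated baseline.** A reader might go further and infer that the baseline is the 0.5 s fixation, spoiled by carry-over from the preceding Probe2 because trials have no gap. The listed events do add up ("Thus, total time per trial = 12.6 sec"). But no section names fixation as the baseline. The same paragraph allows 96–106 trials in 30 min, which is 1800/106 = 17.0 to 1800/96 = 18.8 s per trial. The 4.4 to 6.2 s per trial beyond the listed events may be rests, gaps between trials or both. The supportable defect is that the baseline is undefined.

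**Conclusion.** The concern holds in a limited form. Stage 2 judges active UMI retention by power above an undefined baseline, a measure that the protocol's own Background shows can rise without category information. Neither AMI-against-UMI prediction settles the matter, and the design's own control is not used.

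The size is illustrative: 38% or 78% false findings of an active UMI for a non-specific lift of 0.3 or 0.5 SD at 32 trials per role, and 17% or 38% at 13, against about 2.5% for the not-presented contrast. These rates depend on assumed lifts, SD, independence and balanced roles, none of which the documents give. The 2.5% also assumes that non-specific activity is the same in both roles and that no sample-evoked response remains.

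This is a worthwhile change to settle before analysis, not a flaw that invalidates the study. The not-presented trials are collected in any case, so no data are lost, and the outcomes have no bearing on patient care.

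**What to change.** In Statistical Considerations, Sub-study B, Stage 2:

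- Make this the criterion for active UMI retention: at each category's selected electrodes, and in the same window of the post-cue delay after Cue1, high-gamma power is higher when the category is the UMI than when it was not presented.
- Test AMI against not-presented in the same way as a positive control. Interpret a null UMI result only in patients whose AMI exceeds not-presented.
- Define the baseline and report power against it as descriptive.
- State that the contrast does not remove residual sample-evoked response or non-specific effects that depend on role.

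The change is to wording only; no patients, trials or procedures are added. The cost is precision, because a difference between two sets of trials is noisier than a change from baseline. With balanced roles there are about 32 trials per role from 96, and about 13 from 40. The Sub-study B procedure gives a minimum of 96, while the Data and Safety Monitoring Plan summary gives 40 and Statistical Considerations a minimum of 40. These counts must be reconciled before anyone can say what the contrast can detect.

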As indicated earlier in this protocol, the ECoG study that discovered and characterized the phase-encoded selection mechanism that we will investigate in the present study [70] made this discovery in data from four patients, with a design that yielded 20-30 trials/condition/patient; thus our design, intended to collect a minimum of 40 trials, will be adequately powered to detect effects of interest at the single-subject level. As noted above, however, during his sabbatical year (spent in the lab that published [70]) the PI has observed that as many as double (or more) the final number of subjects desired for an experiment need to be recruited and to participate in it. This is due to several reasons, among them that the ECoG recordings can be contaminated with some much noise that the data are not interpretable, or because a patient’s behavioral performance is too poor. Thus, for this sub-study, we plan to enroll 10 patients, with the intent of needing interpretable data from 4.

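### Sub-study B, Stage 2 defines neither the baseline, nor a trial-level model, nor the balance of cue over sample position, so the precision available from pre-cue power is not secured

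*Combined protocol and SAP*

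**What the plan says.** **Contrast.** In Statistical Considerations, Sub-study B, Stage 2, both AMIs and UMIs are expected to be held actively, "as manifested by above-baseline high-gamma power", and "the amplitude of this high-gamma power will be markedly higher for AMIs". No test, model, covariate or analysis window is given for this comparison. The baseline is mentioned but not defined: it could be fixation or the pre-cue delay, and it could be subtracted or modelled.

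**Timing.** In Research Design and Methods, Sub-study B, the samples are serial: "Sample1 (.5 sec); ISI (.1 sec), Sample2 (.5 sec". They are followed by "Delay1pre-cue (.5 sec), Cue1 (.5 sec), Delay1post-cue (2.5 sec), Probe1 (2 sec".

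**Allocation.** The stimulus description says that "cuing will be randomly determined, such that on each trial one item serves as the AMI". No section states that the cue is balanced over sample position, or that position enters the analysis.

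**Trial numbers.** The procedure section describes a design "intended to collect a minimum of 96 trials, will be adequately powered". Statistical Considerations describes one "intended to collect a minimum of 40 trials, will be adequately powered". Section 1 of the Data and Safety Monitoring Plan also gives 40 trials. Adequacy is argued by analogy with the earlier ECoG study of phase-encoded selection. No effect size, SD, alpha or correlation is stated.

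**The concern.** The cue that makes one item the AMI and the other the UMI is random on each trial, and the pre-cue delay is recorded immediately before it. High-gamma power in that window is therefore a true pre-randomisation measurement. It may carry arousal, slow drift, item strength and residual response to the second sample, all of which would otherwise be unexplained trial-to-trial variance. Sample position is a second such variable, because the two items differ in how recently they were seen when the cue arrives.

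The plan claims adequate power within each patient and needs interpretable data from only four, so trial-level precision carries the claim. Leaving baseline and model open has two consequences. The most efficient valid analysis is not secured. A reader also cannot tell whether the baseline will be subtracted, which can be less precise than not using it at all.

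**Working it through.** **1. The plan's own figures.** There is no power value to reproduce. Trial length does reproduce: 0.5 + 0.5 + 0.1 + 0.5 + 0.5 + 0.5 + 2.5 + 2 + 0.5 + 0.5 + 2.5 + 2 = 12.6 s, as stated. Within the trial, sample 1 ends at 1.0 s, sample 2 at 1.6 s, and Cue1 starts at 2.1 s. The samples therefore end 1.1 s and 0.5 s before the cue.

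**2. Trials per category.** Each trial shows two of three categories, one becoming AMI and one UMI. Each category is expected to be AMI on N/3 trials and UMI on N/3: 32 each at N = 96, about 13 each at N = 40.

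**3. Pre-cue covariate.** rho is assumed. The variance ratio against the unadjusted contrast is (1 − rho²) times the cost of estimating one slope. That cost is 1 + 1/(N − 3) for a within-trial AMI-minus-UMI contrast. For one category across trials it is 1 + 1/(n − 4), with n = 2N/3. A change score has ratio 2(1 − rho), assuming equal pre and post variance.

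| rho | Within-trial, N=96 | Within-trial, N=40 | One category, N=96 | One category, N=40 | Change score |
|---|---|---|---|---|---|
| 0 | 1.011 | 1.027 | 1.017 | 1.044 | 2.0 |
| 0.1 | 1.001 | 1.017 | 1.006 | 1.034 | 1.8 |
| 0.3 | 0.920 | 0.935 | 0.925 | 0.950 | 1.4 |
| 0.5 | 0.758 | 0.770 | 0.762 | 0.783 | 1.0 |
| 0.7 | 0.515 | 0.524 | 0.518 | 0.533 | 0.6 |

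For the within-trial contrast, break-even is rho² = 1/(N − 2): rho = √(1/94) ≈ 0.10 at 96 trials and √(1/38) ≈ 0.16 at 40. Subtracting the pre-cue value is worse than the raw contrast whenever rho < 0.5.

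**4. Position imbalance if cueing is simple random.** The difference between AMI and UMI trials in the share shown second has SD √(0.25/n + 0.25/n), with n trials of each kind. This is √(0.5/32) = 0.125 at 96 trials and √(0.5/13.3) = 0.194 at 40 (0.20 in simulation, where the counts also vary). In simulation, at least one of the three categories is out by more than 20 points in about 26% of patients at 96 trials and 63% at 40.

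**5. Value of a position term.** Let h be half the position effect, in SDs of the within-trial difference (assumed). The ratio is (1 + 1/(N − 3))/(1 + h²).
- h = 0: 1.01 at 96 trials, 1.03 at 40.
- h = 0.25: 0.95 and 0.97.
- h = 0.5: 0.81 and 0.82.

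Forcing balance saves only about 1% (96 trials) to 3% (40) over modelling position after random cueing.

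**6. The two gains overlap.** Simulated at N = 96, rho = 0.5, h = 0.5, the ratios are 0.65 with pre-cue power only, 0.80 with position only and 0.61 with both. With rho = 0.1 and h = 0, using both gives 1.01 at 96 trials and 1.05 at 40.

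**7. Power, as illustration only.** Take a 0.5 SD difference and two-sided 5% (both assumed), treating observations as independent. One category at 32 vs 32 has 50% power unadjusted, and 54%, 62% and 79% at rho 0.3, 0.5 and 0.7. Pooling the three categories at 96 vs 96 gives 93% unadjusted, and 95%, 98% and 99.8%.

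**The case against.** Five points can fairly be made against this.

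- **No unadjusted analysis is stated.** A reader might infer that Stage 2 ignores the pre-cue baseline. The documents do not support that: the same sentence refers to above-baseline power, and no estimator is named. What stands is that baseline and model are undefined.
- **Low power is not shown.** A reader might infer from the 50% figure that the contrast is underpowered. That figure comes from an assumed effect and a one-category split; pooling gives 93% under the same formula.
- **Shared noise may already cancel.** Each trial holds both an AMI and a UMI, so a within-trial difference would remove common arousal and drift. The relevant rho is then that of the difference, and may be smaller. This stands as a limit on the gain. However, Stage 2 specifies no such difference, and Stage 1 selects separate electrodes for each stimulus, so the within-electrode contrast across trials is at least as natural a reading.
- **The window may be a poor covariate.** The pre-cue delay starts when sample 2 goes off, so residual response to that sample could dominate it. This also stands, and is a reason to enter position alongside pre-cue power.
- **Random need not mean simple random.** The wording does not exclude a shuffled balanced list, so the imbalance figures are conditional.

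The setting also tempers the point: Stage 1 is openly exploratory, and Stage 2 rests on phase-amplitude coupling as well, for which no gain has been calculated.

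**Conclusion.** The point holds as one of efficiency and pre-specification. The cue is random, a same-trial pre-cue window exists, and neither a model nor positional balance is stated. A reader might go further and call the contrast biased. It is not: random cueing keeps it unbiased on average, with or without the covariates.

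The size depends on quantities the documents do not give. For rho between 0.3 and 0.7, the pre-cue covariate removes about 8% to 48% of the variance at 96 trials. Near 0.1 it removes nothing. The downside is small: about 1% to 3% per uninformative covariate for the within-trial contrast, up to about 4% for one category at 40 trials, and about 5% for both covariates together at 40. A positional gain needs a real position effect and partly duplicates the pre-cue gain.

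The argument covers the first cue only. The second pre-cue delay follows Cue1 and Probe1, so it is not a clean baseline for the first cue's effect. The change is worth making, but the validity of Stage 2 does not depend on it.

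**What to change.** 1. **Statistical Considerations, Sub-study B, Stage 2.** Define the baseline. Pre-specify, for the Cue1 contrast only, a trial-level analysis of log high-gamma power in the first post-cue delay, within electrode, by cue status of that electrode's item. Include as covariates the same trial's pre-cue power at the same electrode and the item's sample position. Use pre-cue power as a covariate, not as a change score.
2. **Sub-study B stimulus description.** Replace the unspecified random cueing by a random order balanced on category pair (3) × sample order (2) × Cue1 (2) = 12 cells in each run of 12 trials. Each category is then AMI four times and UMI four times per run, twice in each position. This gives 8 full runs in 96 trials, or 3 full runs plus 4 trials in 40, and it limits imbalance if a session stops early. A full crossing that adds Cue2 and both probe matches needs 3 × 2⁵ = 96 cells, so it cannot be completed at 40 trials.
3. **Reconcile the trial minimum:** 96 in the procedure section, 40 in Statistical Considerations and in the monitoring plan. The monitoring plan's 40 trials in 21 min 20 s imply 1280/40 = 32 s per trial, against 12.6 s in the procedure. The trials per condition quoted for the earlier ECoG study also differ (40-50 and 20-30).

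**Cost:** a few sentences of analysis text and a trial-order script, with no added data, time or patients. Cues become slightly more predictable late in a run, and the model spends one or two degrees of freedom.

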The present protocol is motivated by the fact that the work summarized in the Background and Significance section point to two possibilities: a) It may truly be the case that UMIs are not represented by elevated neuronal activity; or, alternatively, b) UMIs are represented by elevated activity that occurs at too fine-grained a scale to be detected with noninvasive imaging methods. Adjudicating between these two possibilities will require an invasive technique that allows for recording neural signals that relate directly to the “elevated activity” that is at the heart of this question. Thus, to continue to make progress on the core question of the neural bases of stimulus representation in working memory, this Revision Application has been prepared to propose pursuing the following “supplement to Aim 1”:

The Specific Aim of this project is to test the hypothesis, with electrocorticography (ECoG) recorded from neurosurgical patients, that unattended memory items (UMIs) are represented in phase angle-segregated patterns of activity in the high-gamma band (80-150 Hz), and that attentional prioritization within working memory is implemented via a mechanism of phase-encoded selection.

This novel hypothesis derives from a recent discovery, with ECoG, from patients performing a task that required the simultaneous maintenance of multiple stimulus-response (S-R) mapping rules: Different rules were found to be represented in prefrontal cortex (PFC) in patterns of high-gamma activity centered on different phase angles of the underlying theta oscillation, and selection among these rules was implemented by dynamic shifts in the phase angle of theta-band coherence between the PFC (where the rules were stored) and M1 (where they were implemented) [70]. Here, we are proposing that analogous mechanisms of phase-segregated representation and phase-encoded selection may also govern the attentional prioritization of one from among multiple items held in working memory.

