#### Statistical Considerations:

Sub-study A: The analyses will proceed in two stages. The first will be to determine the spatial selectivity of each ECoG electrode by calculating its response, in high-frequency (70-250 Hz) broadband power to each of the four locations stimulated during the Receptive Field Mapping task. Also of interest will be fluctuations in alpha-band power (8-13 Hz), and in phase-amplitude coupling (PAC) between alpha-band oscillations in the ECoG signal and high-frequency broadband power.

Data analysis from the Attention Task will focus on electrodes identified in the Receptive Field Mapping task to be preferentially responsive to one, or a subset, of the four critical locations. For each of these electrodes, values of alpha-band power and PAC will be analyzed as a function of attentional condition: attended (i.e., cued with 75% likelihood); ignored (i.e., cued with 25% likelihood); or irrelevant. Although a recent study has looked at alpha-band power as a function of attended vs. ignored [14], the proposed study will differ from this in two important ways. First, our critical comparison is between ignored vs. irrelevant; second, all conditions in our task will be within the same informational domain and sensory modality (i.e., visuospatial perception), whereas that of [14] spanned both (i.e., it used switches between an auditory and a motor task). Because this previous study collected 190 trials per subject [14], we believe that our design, which will collect a total of 384 trials, will be sufficiently powered to carry out the analyses of interest.

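### Sub-study B, Stage 2 attributes higher high-gamma power for attended items to higher PAC, but high-gamma amplitude is an input to PAC and no power control is stated

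*Combined protocol and SAP*

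**What the plan says.** Statistical Considerations, Sub-study B, presents Stage 2 as the test of the phase-encoded selection hypothesis. It makes two linked predictions:

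- **Power:** AMIs and UMIs both show above-baseline high-gamma power, but "the amplitude of this high-gamma power will be markedly higher for AMIs".
- **Mechanism:** "this differential level of high-gamma power will be explained by the fact" that the "electrodes representing the AMI will exhibit higher interregional PAC than will the UMI". The attention-related changes in PAC "may also be concentrated in the alpha band".

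The only description of what PAC combines is in the Sub-study A part of the same section: "phase-amplitude coupling (PAC) between alpha-band oscillations in the ECoG signal and high-frequency broadband power". High-frequency power is therefore one of its two inputs.

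The supplied documents name no PAC estimator, surrogate procedure, matching or adjustment for power, or mediation or time-order analysis. The heading Data analyses and predicted outcomes, in Research Design and Methods, has no text under it. The Data Analysis section removes whole channels with low signal-to-noise ratio, which does not equalise that ratio between AMI and UMI. Stage 1 first tries to select electrodes on high-gamma values.

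**The concern.** The plan predicts a difference in one input to a measure, then reads a difference in the measure as the cause of the first difference. A recorded high-gamma signal contains the activity of interest plus background in the same band. When the activity grows and the background does not, the envelope becomes a cleaner record of whatever modulation is already present. Estimated PAC then rises although the depth of coupling has not changed.

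The central mechanistic inference of Sub-study B is at stake. A higher PAC estimate for AMIs could be reported as evidence that coupling increases with prioritisation, and that this produces the power difference, when only signal strength differed. More trials would not help: this is a bias, and a larger sample only makes it easier to detect.

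**Working it through.** The plan gives no effect size, estimator or test for Stage 2, so there is no figure to reproduce. The check asks whether PAC estimates move when only high-gamma strength moves.

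**Inputs from the documents:** high-gamma band 80-150 Hz (Specific Aims); alpha band 8-13 Hz (Sub-study A); 2.5 s post-cue delay (Research Design, Sub-study B); 1200 Hz sampling; a minimum of 40 trials (Statistical Considerations; the Sub-study B design text gives 96).

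**Assumptions, not in the documents:** coupling depth m of 0 to 0.3, identical in both conditions; background power of 1 in the high-gamma band; signal gain g of 0.7 for the UMI, and 1.0 or 1.41 for the AMI.

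**First-order calculation.** Let the signal be g(1 + m cos φ) times a carrier, plus background of power 1. To first order:

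- In-band power is P = g² + 1, and the signal's share of it is s = g²/(g² + 1).
- The relative modulation of the envelope is about s·m, so a normalised measure scales with s.
- The raw vector length scales with √P · s, and the entropy-based modulation index roughly with s².

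Results:

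- UMI, g = 0.7: P = 1.49; s = 0.49/1.49 = 0.329.
- AMI, g = 1.0: P = 2.00; power ratio 2.00/1.49 = 1.34; s = 0.500; share ratio 0.500/0.329 = 1.52.
- AMI, g = 1.41: P = 2.99; power ratio 2.99/1.49 = 2.01; s = 1.99/2.99 = 0.665; share ratio 0.665/0.329 = 2.02.
- Raw length: √1.34 × 1.52 = 1.76 and √2.01 × 2.02 = 2.87.
- Modulation index: 1.52² = 2.31 and, from the unrounded share ratio 2.023, 4.09.

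**Simulation.** The set-up was 40 trials of 2.5 s, phase taken from a noisy remote alpha signal (so the coupling is interregional), m of 0.1 to 0.3, and 40 replicates per setting. Entries are AMI/UMI ratios of estimated PAC at identical depth.

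| Measure | Power ratio about 1.35: formula | Simulated | Power ratio about 2.0: formula | Simulated |
|---|---|---|---|---|
| Raw vector length | 1.76 | 1.67-1.77 | 2.87 | 2.74-2.86 |
| Normalised vector length | 1.52 | 1.44-1.53 | 2.02 | 1.93-2.01 |
| Modulation index | 2.31 | 1.91-2.20 | 4.09 | 2.81-3.98 |
| Phase-locking value | - | 1.44-1.47 | - | 1.75-1.94 |
| Trial-shuffled z | - | 1.48-2.03 | - | 1.94-2.78 |

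The stronger-gamma condition had the larger PAC in 80-100% of replicate pairs at ratio 1.35 and in 95-100% at ratio 2.0. With equal power the figure is 49% by construction. A separate simulation at a power ratio of about 1.7 gave rises of 1.3- to 2.8-fold on raw, normalised, entropy and shuffled-z measures, in 96-100% of replicates.

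**Where the effect stops.**

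- *Zero coupling, power ratio 2.0:* only raw vector length rises (1.27-fold, larger in 65% of pairs). The other measures do not (42-49% of pairs).
- *No noise floor, power ratio about 2:* s = 1 in both conditions, so the formula gives no change for normalised measures and √2.04 = 1.43 for raw length. Simulated: 0.96-1.09 for the normalised and shuffled measures, 1.40-1.52 for raw length.

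**Does controlling power work, and at what price?** In a further run at a power ratio of about 1.9, matching trials on high-gamma power brought the PAC ratios to 0.85-1.08, with no consistent AMI advantage (33-63% of pairs). About 13 to 15 of 40 pairs were kept at power ratios of roughly 1.7 to 2; at 15, the loss is 25/40 = 62.5%. Retention depends on how much power varies between trials. With 32 trials per condition, signal amplitude doubled and a 5% matching tolerance, no pairs were left when gain was constant. About 2, 8 and 13 were left at assumed log-gain standard deviations of 0.15, 0.3 and 0.5.

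**The case against.** **A power difference alone would produce the finding.** A reader might infer this, or that Stage 2 cannot tell the hypothesis from its alternative at all. Neither is supported. The artefact needs existing coupling together with a noise floor, or else the raw estimator. The Specific Aim also includes segregation of items by phase angle, which is not a contrast of PAC size.

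**Surrogates would take care of it.** A reader might expect z-scoring against shuffled trials to be control enough. It is not: shuffled z rose about 1.5- to 2.8-fold over the power ratios in the table.

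**Interregional PAC is different.** The phase does come from another region, but the amplitude still comes from the electrode whose power is predicted to differ. The simulations used remote phase.

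**PAC that persists at matched power would show that PAC explains power.** It would not. At matched power no difference is left to explain, and under the plan's own hypothesis power lies downstream of PAC. Matching can show only that a PAC difference is not a by-product of power. This objection stands and shapes the fix.

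**Sub-study A has the same problem.** The text does not support this. There, "values of alpha-band power and PAC will be analyzed as a function of attentional condition": power and PAC are parallel outcomes and neither is said to explain the other. The critical contrast is ignored versus irrelevant locations, for which the Background treats the alpha pattern as unsettled.

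**The control may be written elsewhere.** The plan says that its analysis was based on a published ECoG study, and the quality assurance text also points to the grant application. Neither was supplied, so the point is limited to what these documents state.

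**Conclusion.** The concern holds in a conditional form. If coupling is present in both conditions and there is in-band background, a high-gamma power ratio of about 1.35 to 2 raises estimated PAC roughly 1.3- to 4-fold at unchanged depth, and the AMI exceeds the UMI in most or all replicates. The direction is consistent under those conditions. The size is illustrative, because coupling depth, noise floor and power ratio are assumed. Without coupling, or without a noise floor, normalised and shuffled measures are not inflated.

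As written, Stage 2 can therefore give a wrong mechanistic conclusion, and the *explained by* claim has no analysis behind it in the supplied documents. The plan should be changed before analysis.

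**What to change.** In Stage 2, keep the planned AMI versus UMI contrast and add the following:

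1. Fix one PAC estimator before analysis.
2. Repeat the contrast with high-gamma power and low-frequency power controlled, by trial-level power covariates or by power-matched trial subsets with equal trial counts.
3. Conclude that coupling is higher for AMIs only if the difference persists under this control. Otherwise report that the power difference is *accompanied by* higher PAC.
4. Even if it persists, replace *explained by* with *accompanied by* unless a time-order or mediation analysis supports the stronger statement.

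**Cost.** This is wording and code; no new patients or recordings are needed. Matching can discard well over half the trials at a power ratio near 2 (about 15 of 40 pairs kept), so covariate adjustment is the less costly option. Controlling power may also remove some true effect if coupling itself raises power. In the model above, coupling multiplies signal power by 1 + m²/2, which is 4.5% at m = 0.3 and 50% at m = 1; simulated in-band rises were about 4% and 32%. That loss depends on the model, so the unadjusted contrast should still be reported beside the controlled one.
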